1.1. Study Title *

Using combined EEG and non-invasive brain stimulation to examine and improve cognitive control functioning in opioid use disorder

1.2. Is this study exempt from Federal Regulations *

Yes No

1.3. Exemption Number

1 2 3 4 5 6 7 8

1.4. Clinical Trial Questionnaire *

1.4.a. Does the study involve human participants? Yes No

1.4.b. Are the participants prospectively assigned to an intervention? Yes No

1.4.c. Is the study designed to evaluate the effect of the intervention on the participants? Yes No

1.4.d. Is the effect that will be evaluated a health-related biomedical or behavioral outcome? Yes No

1.5. Provide the ClinicalTrials.gov Identifier (e.g. NCT87654321) for this trial, if applicable

Section 2 - Study Population Characteristics (Study 297707)**2.1. Conditions or Focus of Study**

- Opioid use disorder

2.2. Eligibility Criteria

Inclusion criteria will be as follows: 1. Opioid dependent individuals according to the ASSIST opioid dependence score (OUD group, ASSIST opioid Score >12), or healthy controls with no significant history of opioid use (ASSIST opioid Score < 11), or other drug-types (ASSIST score < 11 for each drug category). 2. Native English speakers, 3. Males and Females aged 18-55 years old, 4. Ability to provide informed written or verbal consent, 5. Only participants who clearly understand the research and are able to indicate consent to participate can be enrolled in the study. Exclusion criteria will include uncorrectable visual impairment, uninterrupted central nervous system medication, severe brain injury (traumatic or acquired). Given the nature of the OUD group, opioid users will only be excluded for severe mental health issues (e.g. schizophrenia, bipolar) but not mood disorders such as depression or anxiety, nor will they be excluded for substance abuse. Additional exclusion criteria include any TMS contraindications (e.g., pregnancy, braces, history of seizures).

2.3. Age Limits	Min Age: 18 Years	Max Age: 55 Years
2.3.a. Inclusion of Individuals Across the Lifespan	INCLUSION_LIFESPAN_Study1.pdf	
2.4. Inclusion of Women and Minorities	Women_minorities_children_R21_opioid.pdf	
2.5. Recruitment and Retention Plan	Recruitment_and_Retention_Plan_R21_opioid.pdf	
2.6. Recruitment Status	Recruiting	
2.7. Study Timeline	TIMELINE.pdf	
2.8. Enrollment of First Participant (SEE SECTION 6.3)		

INCLUSION OF INDIVIDUALS ACROSS THE LIFESPAN

Inclusion of Children and Older Adults: We will be including 18-55 year-old individuals in our study. Thus, we will not be including children or older adults in this project. Note that the investigators have had ample previous experience working with participants in this age range, and all study procedures are appropriate for this age range. Children below age 18 and individuals above 55 years old will not be studied in this project because separate age-specific projects are warranted, and even preferred, given that 1) normal developmental changes in reward processes during childhood are prominent but not yet well understood and 2) normal decline in goal-directed processes in older age (above age 55) are known to be prominent but not well understood.

Inclusion of Women, Minorities, and Children

Inclusion of Women: No participant will be excluded on the basis of sex or gender. As described above, participants will be recruited from multiple sources, including student populations and the general community. We will strive for an approximately equal gender balance for the studies proposed here. Given our past inclusion experience, we do not anticipate needing specific outreach programs for recruiting women for this project.

Inclusion of Minorities: No participant will be excluded on the basis of race or ethnicity. As described above, participants will be recruited from multiple sources, including various student populations and the general community. We will make special outreach efforts in recruiting African-American participants for our study, since the College of Arts and Sciences at Rutgers-Newark University where we typically recruit, has an African-American population that under-represents the demographics of Newark, NJ. We have had success in recruiting African-American participants from the general community and from other nearby schools whose enrollment includes a greater number of minority students. Specifically, we will strive to match the demographics of Newark area, which at the time the 2010 census had the following breakdown:

Racial Categories

White 26.31%

Black (African American) 52.35%

Asian (including Pacific Islander / Hawaii Native) 1.62%

American Indian / Alaska Native 0.61%

Other / Unknown 15.22%

More than One Race 3.85%

Ethnic Categories

Hispanic / Latino 33.83%

Inclusion of Children: Previously, NIH considered individuals under 21 years of age to be children, but this has now changed (children are now defined as under 18; see NIH NOT-OD-16-010). We will be including 18- 55 year olds in our study. Thus, we will not be including children in this project. Note that the investigators have had ample previous experience working with participants in this age range (e.g., those 18-20 years old), and all study procedures are appropriate for this age range. Children below age 18 will not be studied in this project because a separate age-specific project is warranted, and even preferred, given that normal developmental changes in cognitive control processes during childhood are prominent, but not yet well understood.

Recruitment and Retention Plan

In total, we plan to collect 60 participants (30 opioid users, 30 controls) over 2 years for the proposed study. Participants will be randomized into TMS or sham groups (15 participants per group). Standard practice in electrophysiological studies commonly use a minimum of 15 participants per experimental group. Further, basing the analyses on our previous results, a priori power analysis indicated that a sample size of 15 would be sufficient to detect a significant effect with a power of .82 and an alpha of .05. Potential OUD participants will be recruited through the community using an 'expression of interest' flyer. The flyer will be distributed throughout pharmacies, clinics, universities, community recreation venues, via email, social networking websites and possibly through media outlets such as through newspapers and radio. Control participants will be recruited using personal networks, advertisements on volunteer job sites and by placing flyers in local community settings.

TIMELINE

Months 1–18. Aim 1 and Aim 2 (initiation) Recruiting and testing control and OUD subjects with our virtual T-maze task with Ri-TMS capabilities, which is already developed.

Months 18–24. Completion of Aim 1 and Aim 2. Analyse data from Months 1–18 for publication. Prepare and submit manuscript for publication.

2.9. Inclusion Enrollment Reports

IER ID#	Enrollment Location Type	Enrollment Location
IER 296360	Domestic	Newark

Inclusion Enrollment Report 296360

1. Inclusion Enrollment Report Title* : Using combined EEG and non-invasive brain stimulation to examine and improve cognitive control functioning in opioid use disorder

2. Using an Existing Dataset or Resource* : Yes No

3. Enrollment Location Type* : Domestic Foreign

4. Enrollment Country(ies): USA: UNITED STATES

5. Enrollment Location(s): Newark

6. Comments:

Planned

Racial Categories	Ethnic Categories				Total	
	Not Hispanic or Latino		Hispanic or Latino			
	Female	Male	Female	Male		
American Indian/ Alaska Native	1	1	0	0	2	
Asian	1	1	0	0	2	
Native Hawaiian or Other Pacific Islander	1	1	0	0	2	
Black or African American	7	8	2	2	19	
White	7	8	5	5	25	
More than One Race	3	3	2	2	10	
Total	20	22	9	9	60	

Cumulative (Actual)

Racial Categories	Ethnic Categories								Total	
	Not Hispanic or Latino			Hispanic or Latino			Unknown/Not Reported Ethnicity			
	Female	Male	Unknown/ Not Reported	Female	Male	Unknown/ Not Reported	Female	Male		
American Indian/ Alaska Native	0	0	0	0	0	0	0	0	0	
Asian	0	1	0	0	0	0	0	0	1	
Native Hawaiian or Other Pacific Islander	0	0	0	0	0	0	0	0	0	
Black or African American	0	3	0	0	0	0	0	0	3	
White	1	4	0	1	1	0	0	0	7	
More than One Race	0	0	0	0	0	0	0	0	0	
Unknown or Not Reported	0	0	0	0	0	0	11	1	12	
Total	1	8	0	1	1	0	11	1	0	
									23	

Section 3 - Protection and Monitoring Plans (Study 297707)

3.1. Protection of Human Subjects [Protection_of_human_subjects_R21_final.pdf](#)

3.2. Is this a multi-site study that will use the same protocol to conduct non-exempt human subjects research at more than one domestic site?

If yes, describe the single IRB plan

3.3. Data and Safety Monitoring Plan [Data_Monitoring_Plan_R21_opioid.pdf](#)

3.4. Will a Data and Safety Monitoring Board be appointed for this study?

3.5. Overall structure of the study team

PROTECTION OF HUMAN SUBJECTS

1. Risks to the Subjects:

1.a. Human Subjects Involvement and Characteristics: The subjects participating in this study will be healthy adults and individuals with opioid use disorder (ages 18 to 55). Participants will be recruited from the Rutgers University-Newark campus and nearby community. Recruitment will be through advertisements posted around the Rutgers University campus, advertising in local media, community forums, clinics and from maintained lists of volunteers interested in repeated participation behavioral studies. We will be seeking a broad sample of adults, such that exclusion criteria will be minimized when possible. Nonetheless, participants will be excluded for the following reasons: 1) taking any medication with potential cognitive effects (e.g., sleeping pills); 2) taking any psychotropic medications (e.g., antidepressants, anti-anxiety agents, anti-psychotics); 3) the presence of any clinically unstable medical disorder, or a medical disorder that affects cognitive or motor function (e.g., epilepsy, Parkinson's Disease); 4) present or past head injury with documented neurological sequelae, and/or causing loss of consciousness, 5) pregnancy; and 6) history of seizures. Note that the Rutgers University- Newark campus and surrounding community have an especially diverse population. Thus, the included participants may involve more diversity than most psychological and neuroscientific studies, possibly allowing for scientific findings that are more representative of the overall population of the nation and the world (see Inclusion of Women, Minorities and Children).

1.b Sources of Materials: All materials for this project will be collected specifically for research purposes. We will collect data regarding brain function using electroencephalography. We will collect behavioral data (reaction times and error rates) based on performance of computer-administered cognitive tasks. Additionally, we may collect self-report information based on personality questionnaires.

1.c. Potential Risks: The potential risks of this project include those associated with routine cognitive testing. The testing instruments to be used for the project are not invasive and pose minimal risk. The testing procedures could induce boredom and fatigue.

There are no known risks associated with TMS when all technical parameters remain within FDA guidelines and the International Federation of Clinical Neurophysiology and the International Society for Transcranial Stimulation, and participants with medical contraindications to TMS are excluded. These guidelines will not be exceeded in the work proposed. The application of TMS may cause the subject some temporary discomfort, such as a mild tingling or minor headache, where the coil is placed on the scalp. An addition risk of TMS is seizures, which has occurred following parameters that exceeded clinical safety guidelines. The current study is in accordance with these guidelines. Robotic neuronavigation for TMS poses minimum risk to the subject. The robotic arm does not touch the patient's head. However, there is a theoretical risk of failure of the computer due to a program "bug". In the unlikely event of a failure, security mechanisms are in place.

There are no known risks associated with EEG. EEGs are safe and painless. The greatest inconvenience is the electrode gel left in subject's hair after the cap is removed, but it can easily be rinsed out at the end of the experiment in the lab, with no damage to the scalp.

2. Adequacy of Protection against Risk:

2.a. Recruitment and Informed Consent: Subjects will be recruited from advertisements and existing subject pools, at Rutgers University and in the surrounding community, to ensure a diverse sample. Consent will be obtained and documented with an institution approved consent form for all subjects. Informed Consent will always be obtained before a subject participates in any component of the current protocol. For all participants, the consent form will be explained to participants as well as having them read the consent themselves. This consent will contain a detailed description of all study procedures, as well as any possible risks and/or benefits. The consent will also indicate (and this will be verbally reinforced by the experimenter) that the participant is free to withdraw from the experiment at any time without penalty or repercussion. Consent will be documented by having the participant and the individuals obtaining consent both sign and date the consent form.

2.b. Protection Against Risk: The routine testing instruments to be used for the project could induce boredom and fatigue. Breaks in experimental sessions will be given whenever the subject requests or obvious fatigue is observed. The motivational incentives and self-disclosing questionnaires could cause anxiety or other negative reactions. Participants will be fully informed of the nature of these experimental components before beginning the session, and explicitly be given the option to decline to participate. Moreover, participants will be assured that their data is being obtained only for research purposes, will only be evaluated in the aggregate, and that all identifying information will be removed (see below).

All of the data collected for these studies will be kept strictly confidential. The person's name and identifying information will be associated with their study ID in a master file that contains no diagnostic information. This

master file will be stored on a computer without Internet access. All other research materials will contain only the participant's study number, and not any identifying information. Only research personnel listed on this application will have access to files containing participant identities. Under no circumstances will individually identifiable data be released to anyone without the expressed written consent of the participant. In the past we have found that all of these procedures are effective at reducing risk for study participants.

To ensure safe practices in the event of any side effects of TMS exhibited by the subjects, [name], MD (a neuroradiologist and Director of Radiology at New Jersey Medical School, Rutgers Newark), will work on this project as the contact physician. In the event of a seizure, there is no need to go more than just stay with the participant and monitor them for up to an hour for signs of post-seizure confusion. Seizures are thought to be caused by group of neurons that become hyper-synchronized and are categorized as "absent-type", which cause lapses in awareness, sometime with staring, and last less than a few seconds. In some cases, confusion post-seizures to be expected up to 30 minutes, max. No one has ever developed a recurring seizure disorder (epilepsy) after a TMS-induced seizure. Any side effects exhibited by subjects will be reported to [name] before they leave the lab. If post-seizure confusion exceeds 30 minutes, and after consulting with [name], we will advise and accompany the participant to the University Hospital Emergency Room for safety. We will have subjects fill out a short questionnaire at the end of sessions to formally track and document any adverse side effects which may occur.

In the unlikely event of a computer failure during robot-guided TMS, security mechanisms are in place: There is an immediate shut off button held by the subject, the experimenter, and one on the robotic arm itself. Once the button is pressed, the arm will stop immediately without movement and will remain in the position where it stood at the time.

3. Potential Benefits of the Proposed Research to the Subject and Others: There will be no direct benefits to individuals for participating in this proposed project, other than the knowledge that they are contributing to our understanding of human cognitive and motivational processes and their biological underpinnings. However, the risks of this project are relatively small. If successful, substantial knowledge will be gained about cognitive control deficits associated with OUD. Furthermore, a closer examination of the role of TMS in modulating ACC activity may advance clinical research and treatment development of OUD. In consideration of the small risks and substantial scientific benefit of this work, we consider the risk/benefit ratio to be favorable.

4. Importance of Knowledge to be Gained: Cognitive control is critical component of human behavior, and the breakdown of this process in OUD may contribute to relapse and treatment failure in this group. A better understanding impaired reward processing via electrophysiological methods may highlight a highly sensitive biomarker of addiction severity and treatment efficacy. Further, stimulation of a dysfunctional ACC network may help to restore cognitive control functioning in opioid users, and may therefore have promising future applicability for addiction research. As noted above, the risks of this project are relatively small, and not appreciably greater than the risks of ordinary computerized testing and imaging procedures. Thus, given that the risks to participants in this study are small, we believe such risks are reasonable in relation to the importance of the knowledge that we will gain about the psychological and neural mechanisms of cognitive control in OUD.

Human Subjects Education: In accordance with the NIH policy effective October 1, 2000, this is to certify that all key personnel involved in the design and conduct of the human subjects research aspect of the above referenced grant have been educated on the protection of human research participants.

Data safety and monitoring plan

Participant confidentiality. Participants' records will be kept strictly confidential. Confidentiality will be ensured by assigning a random ID number to each participant. Identifying information will be maintained only in a password-protected database. All other data and records will contain only the ID number. Electronic data will be accessed via password-protected computers that are available only to the PI and co-PIs for this study. Long-term storage will be necessary to provide sufficient time for follow-up analysis and publication of deidentified data. The link between identifiable information and test data, as described in part "2b" above, will be stored exclusively in a password-protected database accessible only by the PI and co-investigators for this study.

Participants will also be protected by a Certificate of Confidentiality, which will be obtained from the NIH. This Certificate can be used by the researchers to legally refuse to disclose information that may identify participants in any federal, state, or local civil, criminal, administrative, legislative, or other proceedings, for example, if there is a court subpoena. The researchers will use the Certificate to resist any demands for information that would identify participants, except in cases where information is requested by personnel of the United States federal or state government agency sponsoring the project and that will be used for auditing or program evaluation of agency funded projects or for information that must be disclosed in order to meet the requirements of the federal Food and Drug Administration (FDA). The Certificate of Confidentiality will not be used to prevent disclosure to state or local authorities of child abuse and neglect, or harm to self or others.

Section 4 - Protocol Synopsis (Study 297707)

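### The seizure instruction plans only for a brief absence-type lapse: any other seizure has no written route to emergency care unless confusion outlasts 30 minutes, and release does not require recovery

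*Protocol*

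**What the plan says.** The seizure procedure is one paragraph in the Protocol, under Protection of Human Subjects, 2.b (Protection Against Risk). It first appoints a contact physician for TMS side effects. It then says:

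- **Response.** In a seizure, "there is no need to go more than just stay with the participant and monitor them for up to an hour". The watch is directed at one sign: staff "monitor them for up to an hour for signs of post-seizure confusion".
- **Assumed seizure.** Seizures are placed in an absence-type category, "which cause lapses in awareness, sometime with staring, and last less than a few seconds". Confusion may follow in some cases and is expected to last at most 30 minutes.
- **Reporting.** "Any side effects exhibited by subjects will be reported to" the contact physician, and this is due before the participant departs.
- **Emergency care.** "If post-seizure confusion exceeds 30 minutes, and after consulting with" the physician, "we will advise and accompany the participant to the University Hospital Emergency Room for safety".
- **Documentation.** "We will have subjects fill out a short questionnaire at the end of sessions", to record adverse effects.

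Section 1.c (Potential Risks) names the hazard without limiting its type: "An addition risk of TMS is seizures, which has occurred following parameters that exceeded clinical safety guidelines". It adds that this study stays within those guidelines.

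**The concern.** A contingency instruction has to work for the cases that go badly. This one is built around the mildest presentation, and it tells staff that staying and watching is enough. If a seizure were convulsive, prolonged or repeated, someone following the text would find no step that leads to emergency care unless confusion persisted past half an hour. The text also does not say what state a participant must be in before going home.

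What is at stake is participant safety. Seizure is the most serious TMS harm named in section 1.c, and section 3 of the same attachment says that participants gain no direct benefit. The analysis, the sample size and the primary outcome are not affected.

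**Working it through.** No formula applies and the plan has no figure to reproduce. The check sets the statements in the 2.b paragraph against each other, then looks for repair elsewhere.

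**1. The times.** The paragraph gives four: a seizure of a few seconds at most, expected confusion of up to 30 minutes, an emergency-room trigger above 30 minutes, and a watch of up to 60 minutes. The 30-minute trigger lies inside the 60-minute watch, so these times do not conflict. Two things follow from them:

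- The trigger starts where the expected course ends. Confusion is expected to last no more than 30 minutes, and transfer needs more than 30. The only written route to emergency care is therefore for an event that the paragraph does not expect.
- Sixty minutes is a ceiling with no floor. A watch shorter than 30 minutes would comply with it.

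**2. A seizure that fits the description.** A brief lapse followed by short confusion is handled: staff stay, watch and report. If confusion passes 30 minutes, escorted transfer follows. For this case the plan is workable.

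**3. A seizure that does not fit.** Take a convulsive, prolonged or repeated seizure with confusion that clears within 30 minutes. The watch is for confusion and the trigger is confusion, so the transfer condition is never met, whatever the seizure's length or number. The paragraph has no condition based on seizure type, duration, recurrence or injury. The remaining duty is to report to the physician before departure, with no requirement to do so when the seizure occurs.

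**4. Leaving the laboratory.** The one step required before departure for any side effect is the report to the physician. It is a notification. The text does not say that confusion must have resolved or that the physician must agree to release.

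**5. Repair elsewhere.**

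| Place | What it contributes |
|---|---|
| Protocol 2.2; Protection of Human Subjects 1.a | Exclude people with a history of seizures: prevention, not response |
| Protection of Human Subjects 1.c | Names the risk and commits to the guidelines; no procedure |
| 2.b, the paragraph after the seizure text | Shut-off buttons, described for a computer failure of the robot |
| Data safety and monitoring plan | Covers confidentiality; no seizure procedure |
| SAP | Silent on the point |

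None of these adds an emergency route or a recovery condition.

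**The case against.** The strongest reply is that the paragraph should be read whole. The instruction to stay and watch comes after the contact physician has been introduced, and the sentences that follow qualify it with a report, an escorted transfer and a questionnaire. The physician must hear of every side effect of whatever type, so escalation can happen without the confusion trigger. People with a history of seizures are excluded and stimulation stays within guidelines. The text is also an attachment to a grant application, and nothing says it is the procedure used at the chairside.

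Much of this stands, and it rules out several stronger readings:

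- *The paragraph contradicts itself.* A reader might infer this because the instruction says nothing more is needed and further steps then follow. The steps can all be carried out in sequence, and the questionnaire is routine for every session. The wording is misleading but not contradictory.
- *Emergency help before 30 minutes is barred.* The text does not say so. It only fails to provide for it.
- *Consultation adds delay on top of the 30 minutes.* The text does not say that consultation must wait until 30 minutes have passed; it could take place during the watch. The documents support no figure for added delay.
- *Nothing stands between a seizure and going home.* The report before departure is required. What is missing is a recovery or clearance criterion.
- *Staff would act on this sentence first.* The documents do not show which text staff use in an emergency.

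The reply does not remove the central point. The report has no timing beyond departure, the physician is a contact who is not stated to be present, and the one written transfer route depends on confusion alone. Low likelihood does not answer this either, because the instruction exists for the unlikely event.

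**Conclusion.** The concern holds as a defect in a stated safety rule. The plan has one written route to emergency care, with two conditions (confusion beyond 30 minutes, and consultation), and it states no recovery or clearance condition for release. Followed as written, it serves a brief absence-type lapse and leaves other seizures without a written emergency route when confusion clears within 30 minutes.

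This rests on one assumption: that a seizure outside the paragraph's description can occur. Section 1.c does not limit the type, but the documents give neither a rate nor a breakdown by type, so no probability or expected number of events is claimed. The existing safeguards (exclusion of seizure history, stimulation within guidelines, contact physician, report before departure, escorted transfer) reduce the risk without correcting the rule. The rating is should-fix, at the low end.

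**What to change.** Amend the one paragraph in 2.b as follows:

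1. Delete the wording that tells staff they need only stay with the participant.
2. Notify the contact physician of any seizure when it occurs, not merely before departure.
3. Allow release only once confusion has resolved. The physician and the IRB should set the observation time.
4. Send any seizure that is not a brief absence-type lapse directly to emergency care.
5. State that transfer does not wait on reaching the physician.

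The cost is a one-paragraph protocol amendment with IRB review. It adds no participants, visits or procedures, and uses staff time only if a seizure occurs. The analysis plan is unchanged.
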